16.1.4.5 Programming rules

The following should be used for programming of efficacy results:

16.1.4.5.1 Calculation of 'time to event' variables

Time to event = end date - start date + 1 (in days)

When no post-baseline tumor assessments are available, the date of randomization/start of treatment will be used as end date (duration = 1 day) when time is to be censored at last tumor assessment, i.e. time to event variables can never be negative.

16.1.4.5.2 Incomplete assessment dates

All investigation dates (e.g. X-ray, CT scan) must be completed with day, month and year.

If one or more investigation dates are incomplete but other investigation dates are available, this/these incomplete date(s) are not considered for calculation of the assessment date (and assessment date is calculated as outlined in [Section 16.1.3.2.8](#)). If all measurement dates have no day recorded, the 1st of the month is used.

If the month is not completed, for any of the investigations, the respective assessment will be considered to be at the date which is exactly between previous and following assessment. If a previous and following assessment is not available, this assessment will not be used for any calculation.

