6.1.4.1 Treatment beyond disease progression

Following approval of protocol amendment 03, treatment with pembrolizumab will strictly adhere to the drug's approved label for the study indication. Accordingly, pembrolizumab may be administered until disease progression, unacceptable toxicity, or up to 35 cycles in subjects without disease progression, whichever occurs first. Treatment beyond disease progression will no longer be allowed as part of this study.

Subjects who have documented disease progression per RECIST 1.1 can remain on study treatment if they meet all the following criteria after documented discussion and agreement between the investigator and the Novartis medical monitor. Subjects are to be informed by the investigator of the options to continue study treatment as well as of other therapeutic options and their benefits, should they exist.

- Clinical benefit per investigator's judgement (e.g. tumor shrinkage at other sites or symptomatic improvement)
- Continuation of treatment beyond initial progression will not delay an imminent intervention to prevent serious complications of disease progression
- Subject exhibits adequate tolerance to study treatment
- Subject performance status is stable
- Absence of symptoms and signs (including worsening of clinically relevant laboratory values) indicating disease progression

Subjects who meet the above criteria and continue study treatment beyond initial disease progression per RECIST 1.1 (see [Section 16.1](#)) [REDACTED] and continue all study procedures as outlined in [Table 8-2](#).

In case of clinical deterioration or suspicion of disease progression, a follow-up imaging assessment should be performed promptly rather than waiting for the next scheduled assessment.

[REDACTED]

Please refer to [Section 8.3](#) for additional information on RECIST 1.1 [REDACTED].

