Imaging assessments as described in [Table 8-3](#) should be performed at the time points specified using the same imaging modality used at baseline, irrespective of study treatment interruption or actual dosing (see [Table 8-2](#)). Imaging assessments for response evaluation will be performed every 9 weeks (+/- 7 days) through 45 weeks and every 12 weeks (+/- 7 days) thereafter until disease progression, death, lost to follow-up or withdrawal of consent. Imaging assessments should be scheduled using the randomization date as the reference date (not the date of the previous tumor assessment) and should be respected regardless of whether treatment with study treatment is temporarily withheld or unscheduled assessments performed.

Additional imaging assessments may be performed at any time during the study at the investigator's discretion to support the efficacy evaluations for a subject, as necessary. Clinical suspicion of disease progression at any time requires a physical examination and imaging assessments to be performed promptly rather than waiting for the next scheduled imaging assessment.

Each lesion that is measured at baseline must be measured by the same method (either same imaging method or by photography, including a metric ruler) and when possible, the same local radiologist/physician throughout the study so that the comparison is consistent. If an off-schedule imaging assessment is performed because progression is suspected, subsequent imaging assessments should be performed in accordance with the original imaging schedule.

Combined PET/CT may be used only if the CT is of similar diagnostic quality as a CT performed without PET, including the utilization of IV contrast media. At the discretion of the Investigators, FDG-PET scans may be performed to document progressive disease per RECIST 1.1 ([Section 16.1](#)).

The coded medical images will be used primarily for analysis as described in this protocol; however, the images may also be used for the development and evaluation of new analysis methods directly related to the area of research that this study covers.

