11.2 Database management and quality control

Novartis personnel (or designated CRO) will review the data entered by investigational staff for completeness and accuracy. Electronic data queries stating the nature of the problem and requesting clarification will be created for discrepancies and missing values and sent to the investigational site via the EDC system. Designated investigator site staff are required to respond promptly to queries and to make any necessary changes to the data.

Concomitant treatments and prior medications entered into the database will be coded using the WHO Drug Reference List, which employs the Anatomical Therapeutic Chemical classification system. Medical history/current medical conditions and AEs will be coded using the Medical Dictionary for Regulatory Activities (MedDRA) terminology.

Randomization codes and data about capmatinib dispensed to the subject and all dosage changes will be tracked using Interactive Response Technology (IRT). The data will be used for analyses specified in [Section 12](#).

Once all the necessary actions have been completed and the database has been declared to be complete and accurate, it will be locked **and the treatment codes will be unblinded** and made available for data analysis/moved to restricted area to be accessed by independent programmer and statistician. Any changes to the database after that time can only be made after written agreement by Novartis development management.

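### The missing-month rule for tumour assessments preferentially discards undated progression scans, so a known progression can become a censored observation; the bias in PFS and DOR is upward but probably very small

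*Protocol*

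**What the plan says.** Protocol Section 16.1.4.5.2 deals with incomplete scan dates in steps.

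- It starts from a requirement: "All investigation dates (e.g. X-ray, CT scan) must be completed with day, month and year".
- If some dates at an evaluation are incomplete and others are available, "this/these incomplete date(s) are not considered for calculation of the assessment date".
- If only the day is missing throughout, the first of the month is used.
- For a missing month the text reads "If the month is not completed, for any of the investigations, the respective assessment will be considered to be at the date", and the date is the midpoint: "the respective assessment will be considered to be at the date which is exactly between previous and following assessment".
- The last step is the discard: "If a previous and following assessment is not available, this assessment will not be used for any calculation".

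Protocol Section 8.3.1 schedules imaging every 9 weeks through week 45 and every 12 weeks "thereafter until disease progression, death, lost to follow-up or withdrawal of consent". Under Protocol Section 12.4.1.3 and SAP Section 2.5.3, a subject without a usable event is censored at the last CR, PR or SD assessment, or at randomisation if there is none.

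SAP Section 5.1 imputes dates for dosing, adverse events, medications, prior and later therapies, and diagnosis. It has no rule for tumour assessments, so the protocol appendix is the only stated one.

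**The concern.** The discard depends on whether a later scan exists, and that depends on the outcome. Imaging normally ends with the progression scan, so that scan has no following assessment. If its month is missing, the progression leaves the analysis and the subject is censored at an earlier scan. The progression itself is certain; only its date is in doubt.

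Other rules in the same documents keep the event and impute its date. A death with a missing day is set to the 15th (Protocol Section 16.1.4.5.3), and an adverse event of uncertain timing is counted as on-treatment (SAP Section 5.1.2).

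PFS is the primary endpoint and DOR follows its censoring rules, so both would be pushed upward. Losing a PD does not change ORR or DCR: a best response that falls from PD to unknown counts in neither.

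Two phrases can also be programmed in more than one way. One is whether the month rule is triggered by a single undated investigation or only when none is usable. The other is whether the discard needs one neighbour to be missing or both.

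**Working it through.** The documents give no rate of missing months and no figure for this rule, so there is no stated result to reproduce.

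**1. Trace of the rule**, taking baseline as an admissible earlier neighbour and discarding when either neighbour is absent:

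| Assessment without a month | Later scan? | Result |
|---|---|---|
| CR/PR/SD, not the last scan | yes | kept at midpoint |
| CR/PR/SD, last scan | no | discarded; censoring moves earlier |
| PD, imaging stopped | no | discarded; event becomes censored |
| PD, scanned again | yes | kept at midpoint |

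If the discard instead needs both neighbours to be missing, the third row has no midpoint and no instruction. The progression still receives no date.

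**2. Check of the PFS model** (Protocol Section 16.3.2.1: change at day 64, 75% progression-free then). With second-period hazard −ln(0.5/0.75)/(median − 64 days), HR2 = (control median − 64)/(combination median − 64), using 30.4375 days per month. For 12.8 vs 8.5 months: (258.7 − 64)/(389.6 − 64) = 0.598. The other three scenarios give 0.505, 0.496 and 0.500, against 0.505, 0.496 and 0.501 in Protocol Table 12-2.

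**3. Simulation**, 40,000 subjects per scenario, with the protocol's scan schedule and ±7-day window. Assumptions not in the documents: the month is missing at random with probability p, equally for all scans and for the whole assessment; follow-up is uniform over 3 to 15 months; all events are progressions; there is no dropout.

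- Final scans are 22.4%, 23.2% and 23.9% of all CR/PR/SD scans at true medians of 7.1, 8.5 and 10.3 months. That is the share of undated CR/PR/SD scans discarded.
- With no imaging after progression, 100% of undated PD scans are discarded. The ratio is about 1/0.232 = 4.3 to 1.
- If 30% of progressing subjects are scanned again, 70% are discarded. The ratio is about 0.70/0.232 = 3.0 to 1.

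Effect on PFS at a true median of 8.5 months, no scan after progression:

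| p | KM median (months) | 12-month PFS |
|---|---|---|
| 0 | 8.37 | 0.381 |
| 1% | 8.38 | 0.383 |
| 2% | 8.39 | 0.385 |
| 5% | 8.43 | 0.391 |
| 10% | 8.48 | 0.402 |

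The median moves by 8.43 − 8.37 = 0.06 month at 5% and 8.48 − 8.37 = 0.11 at 10%. At true medians of 7.1 and 10.3 months the shifts are 0.07 and 0.06 at 5%, and 0.14 and 0.14 at 10%.

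**4. Expected events lost.** With 51 + 25 = 76 subjects and the simulated event rate of 0.468, about 36 progress. The expected loss is 36p: 0.4 at 1%, 0.7 at 2%, 1.8 at 5%, 3.6 at 10%.

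**5. One first-scan PD lost among 25 controls.** The subject is censored at day 1. With no other early censoring, the KM estimate changes from (25 − d)/25 to (25 − d)/24 after d first-scan progressions. The gain is therefore S/24 at any later time: 0.76/24 = 3.2 points, 0.5/24 = 2.1, 0.3/24 = 1.3.

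**The case against.** The strongest answer is that the trigger should hardly occur. Complete dates are mandatory, and under Protocol Section 11.2 a query for "clarification will be created for discrepancies and missing values and sent to the investigational site via the EDC system". Section 11.3 requires source verification of data for primary variables. Before amendment 03, images were also collected and quality-checked centrally. This stands and is the main reason the effect is small. The rule exists for whatever remains after queries.

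PFS is now descriptive, with no test (Protocol Section 12.4.1.2), and the rule is the same in both arms. That also stands: nothing here shows a bias between arms. The derivation specifications named in the SAP introduction were not supplied, so the programmed rule may differ from the stated one.

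A reader might infer more than the documents support:

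- *That the rule deletes only progressions and keeps every stable or responding scan.* It does not look at response. The final CR, PR or SD scan of a subject without progression is dropped too, and 50 subjects were still on treatment on 15-Mar-2021.
- *That every undated progression is lost.* Before amendment 03, "Subjects who have documented disease progression per RECIST 1.1 can remain on study treatment if they meet all the following criteria"; those subjects continued study procedures, so a later scan could exist. A later death can also count as an event. That rescue is partial: survival follow-up has stopped, and deaths after two or more missed assessments, or after the capmatinib decision in the combination arm, are censored.
- *That one undated bone scan removes a progression with a fully dated CT.* The preceding paragraph of Section 16.1.4.5.2 sets incomplete dates aside when others are available. The month rule can be read as the residual case where none is usable. The wording is unclear, but it does not establish the harsher reading.
- *That one lost event lifts the control curve by a constant 4 points.* The gain is S/24. It reaches 4.0 points only at S = 0.96 and shrinks as the curve falls.

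**Conclusion.** The point holds as a minor one. As written, the rule removes nearly all undated progression scans unless a later scan exists, against roughly a quarter of undated CR, PR or SD scans. A known progression can thereby become a censored observation, and the net effect on PFS and DOR is upward.

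The size is probably very small: under 0.1 month on median PFS at up to 5% missing months. I assume 0 to 2 affected subjects; two of about 36 progressions would be 2/36 = 5.6%. The true rate is not in the documents. The figures rest on months missing at random, discard when either neighbour is missing, and the follow-up pattern assumed above. The direction needs only that imaging usually ends at progression. The two ambiguities are worth settling in any case, because they affect how the primary endpoint is programmed.

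**What to change.** Add to the SAP imputation section, before database lock:

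1. The month rule applies only when no investigation at that evaluation has a usable date. Otherwise the complete dates are used. For other assessments, state whether the discard needs one neighbour or both to be missing.
2. A PD is never dropped because its date is incomplete. If there is no following scan, date it at the planned day for that evaluation, counted from randomisation. The date may not precede the day after the previous assessment, nor pass the earliest of death, last contact or data cut-off. If no contact is recorded after the previous assessment, the lower bound applies. Keep the PD as an event, subject to the existing censoring rules.

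End of treatment should not be an upper bound. Before amendment 03, subjects who stopped treatment for other reasons were still scanned until progression (Protocol Section 9.2.2.2), so a cap there would move a genuine later progression forward in time.

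The cost is a few lines of text and a minor programming change, with no new data. The downside is an imputed event date for any affected subject, which should be flagged in the listing. In the combination arm that date can also decide whether the PD falls before or after the sponsor's capmatinib decision. A count of assessments without a month would show whether the rule is ever used.

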16.1.4.5.3 Incomplete dates for last known date patient alive or death

All dates must be completed with day, month and year. If the day is missing, the 15th of the month will be used for incomplete death dates or dates of last contact.

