2.1.1.6 Last contact date

The last contact date will be derived for subjects not known to have died at the analysis cut-off using the last complete date among the following data sources ([Table 2-1](#)).

Table 2-1 Last contact date data sources

Source data	Conditions
Last contact date/last date subject was known to be alive from Survival eCRF page	Patient status is reported to be alive or unknown in the survival eCRF page
Start/End dates from further antineoplastic therapy	Non-missing medication/procedure term
Start/End dates from study treatment eCRF	Non-missing dose. Doses of 0 are allowed.
End of treatment date from end of treatment page	No condition.
Tumor (RECIST) assessment date	Evaluation with a response
Date of verification for treatment beyond RECIST 1.1 Progressive disease.	Will the subject continue treatment beyond disease progression as per RECIST 1.1? marked as 'Yes'
PK collection dates	Was sample taken marked as 'Yes'
Vital signs/ECGs/Laboratory date	At least one non-missing parameter value
Performance Status date	Non-missing performance status

Source data	Conditions
Start/End dates of AE	Non-missing verbatim term

The last contact date is defined as the latest complete date from the above list on or before the data cut-off date. The cut-off date will not be used for last contact date, unless the subject was seen or contacted on that date. No date post cut-off date will be used. Completely imputed dates (e.g., the analysis cut-off date programmatically imputed to replace the missing end date of a DAR) will not be used to derive the last contact date. Partial date imputation is allowed for event (death)/censoring is coming from 'Survival information' eCRF.

The last contact date will be used for censoring of subjects in the analysis of OS.

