2.5.1 Definition of primary endpoint

PFS is defined as the time from the date of randomization to the date of the first documented progression or death due to any cause. PFS will be assessed via local review according to RECIST 1.1.

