2.7 Analysis of secondary objectives

2.7.1 Secondary endpoints

The secondary efficacy endpoints are ORR, DCR, TTR, DOR as per RECIST 1.1 and OS. Estimation of all secondary endpoints will be provided by treatment arms based on the FAS. All relative listings, tables and figures will be presented by treatment arm, unless otherwise specified.

Objective response rate (ORR)

ORR is defined as the proportion of subjects with a BOR of CR or PR as per local review and according to RECIST 1.1.

BOR is defined as the best response recorded from the start of the treatment until disease progression/recurrence as per local review and according to RECIST 1.1.

Disease control rate (DCR)

DCR is defined as the proportion of subjects with a BOR of CR, PR or SD as per local review and according to RECIST 1.1.

Time to response (TTR)

TTR applies to all subjects. For responders, TTR is defined as the time from the date of randomization to the first documented response of either CR or PR, which must be subsequently confirmed (although initial date of response is used, not date of confirmation). For non-responders, TTR will be censored at the last adequate tumor assessment date if no PFS event occurs, otherwise, TTR will be calculated at the censored time from the first visit of the first subject to the last visit of the last subject.

Duration of response (DOR)

DOR is defined as the time between the date of first documented response (CR or PR) and the date of first documented progression or death due to underlying cancer.

Overall survival (OS)

OS is defined as the time from randomization to date of death due to any cause.

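### A death date with a missing day is set to the 15th of the month with no lower bound, so it can fall before a date on which the subject was known to be alive, or before randomisation

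*Protocol*

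**What the plan says.** Protocol Appendix 1, section 16.1.4.5.3, opens with a requirement, "All dates must be completed with day, month and year", and then gives the fallback: "If the day is missing, the 15th of the month will be used for incomplete death dates or dates of last contact". It does not compare the imputed date with any other date. Section 16.1.4.5.1 computes every time-to-event variable in days as end date minus start date plus 1.

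SAP 2.1.1.6 accepts such dates: "Partial date imputation is allowed for event (death)/censoring is coming from 'Survival information' eCRF". It gives no algorithm and no limit. The last contact date defined there is derived only for subjects who are not recorded as dead, so it cannot act as a floor for a death date. SAP 5.1 has imputation rules for study drug, adverse events, concomitant medication, prior and post therapies and diagnosis dates, but none for death. SAP section 4 reports no departure from the protocol analyses, so the protocol rule stands.

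The death date enters two efficacy endpoints. In SAP 2.7.1, "OS is defined as the time from randomization to date of death due to any cause". In SAP 2.5.1, PFS ends at "the date of the first documented progression or death due to any cause".

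**The concern.** Followed literally, the rule can produce impossible records. A subject with a stable-disease scan on 24 November and a death recorded only as November gets an OS and PFS event on 15 November, nine days before a scan that showed no progression. A subject randomised on 20 October who dies that October gets a death date five days before randomisation.

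Other imputations in the same SAP are guarded. The last-dose date is checked against the start of its record (5.1.1.1). An adverse event that starts after treatment start, or possibly so, cannot be placed before the day after the first dose (5.1.2). Prior-therapy end dates are capped (5.1.3.1), and post-therapy start dates have a floor (5.1.3.2). The date that defines OS, and can define a PFS event, has no such check. A programmer must then either output an impossible date or make a correction that the protocol and SAP do not describe.

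**Working it through.** **Inputs.** The 15th-of-month rule (Protocol 16.1.4.5.3); time = end - start + 1 (Protocol 16.1.4.5.1); months of 28 to 31 days.

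**The plan's own figure.** Section 16.1.4.5.1 gives a duration of 1 day when the end date equals the randomisation date. The formula gives 0 + 1 = 1 day, so it is reproduced.

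**Error of the rule over a whole month.** If the true day of death is d, the error is 15 - d. With d equally likely over a month of L days, the mean error is 15 - (L + 1)/2.

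| Month length | Error range (days) | Mean error (days) |
|---|---|---|
| 28 | -13 to +14 | +0.5 |
| 29 | -14 to +14 | 0.0 |
| 30 | -15 to +14 | -0.5 |
| 31 | -16 to +14 | -1.0 |

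**Error when the subject is known alive after the 15th.** Then d is at least 16 and at most 31, so 15 - d runs from -1 to -16. In these cases the time is always too short.

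**Death in the month of randomisation.** With randomisation on day r, the time is 15 - r + 1 = 16 - r. It is 0 for r = 16, negative from r = 17, and -15 for r = 31.

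**Worked records, with the bound max(15th, last alive date, randomisation date).**

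| Randomised | Last known alive | True death | True time | Rule as written | Bounded |
|---|---|---|---|---|---|
| 20 Oct 2020 | 22 Oct | 29 Oct | 10 | 15 - 20 + 1 = -4 | 22 - 20 + 1 = 3 |
| 1 Jun 2020 | 26 Oct | 30 Oct | 152 | 137 | 148 |
| 1 Jun 2020 | 3 Oct | 30 Oct | 152 | 137 | 137 |

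The third record has no conflict, and the bound leaves it unchanged.

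**How often a conflict arises.** The documents give no figure, so this is an assumption: death is uniform over calendar days, and the gap from the last alive date to death is uniform from 0 to G days. By simulation, the share of missing-day deaths placed before a known-alive date is:

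| G (days) | Share in conflict |
|---|---|
| 7 | 39% |
| 14 | 28% |
| 21 | 19% |
| 30 | 14% |
| 63 | 7% |

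With contact every 84 days, as in the former 12-weekly survival calls, the share is about 5%. The imputed death precedes the alive date by about 6 to 7 days on average. For contact intervals of 21, 42 and 84 days, bounding at the last alive date lowers the mean absolute error from 7.6 days to between 6.5 and 7.3 days, a gain of 0.3 to 1.1 days per missing-day death.

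**The case against.** The best defence is that the rule will rarely be used and that a safeguard may exist elsewhere. Complete dates are required, the eCRF is checked automatically and missing values are queried (Protocol 11.1 and 11.2), and data for primary variables are fully verified (11.3). Derived-variable specifications are in a separate programming document that is not available here, and Protocol 16.1.4 calls its rules guidance, with programs to be adapted for each study. The analyses are descriptive Kaplan-Meier summaries of 76 randomised subjects. All of this stands. It limits the point to what the protocol and SAP state; it does not show that the final datasets will contain negative times.

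A reader might infer three stronger things that the documents do not support.

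- **That the rule contradicts section 16.1.4.5.1**, which says that "time to event variables can never be negative". That clause closes a sentence about censoring when there is no post-baseline tumour assessment: "when time is to be censored at last tumor assessment, i.e. time to event variables can never be negative". In that context it does not govern death events. It is therefore not contradicted, and it does not protect against a negative time either.
- **That the rule shortens survival in general.** Over a whole month the mean error is within about one day of zero, and a time can also be up to 14 days too long. The shortening belongs to the conflict cases.
- **That deaths on treatment bear most of the error.** Contacts are closer then, but the day of death is also more likely to be known. Protocol 10.1.3 requires SAEs up to 30 days after the last dose to be reported within 24 hours, although 10.1.1 generally exempts documented progression. A missing day is more plausible for a death learned of at a 12-weekly survival call, where the conflict rate is lowest, and those calls ended with amendment 03.

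**Conclusion.** The rule as stated is faulty in a definable set of cases, and the SAP does not repair it. When a subject is known alive after the 15th of the death month, the imputed death contradicts the database and OS is 1 to 16 days too short. PFS is affected in the same way when death is the event. When death falls in the month of randomisation and randomisation was on the 16th or later, the time is 0 to -15 days. The same imputed date can also cut short the exposure duration in SAP 2.4.1.1, which is truncated at death.

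These ranges follow from the calendar and the stated formula alone. The conflict frequencies rest on the assumed contact gaps above. The number of missing-day deaths is not given and is probably small. No hypothesis test depends on the rule, and a material change in a reported median is unlikely. This is a small correction, worth making because it prevents impossible records and undocumented repairs at almost no cost.

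**What to change.** Add a death-date rule to SAP 5.1. When only the day is missing, the imputed date is the latest of (a) the 15th of the recorded month, (b) the latest complete date in that month on which the subject was demonstrably alive, and (c) the randomisation date. The resulting time is then at least 1 day.

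Derive the alive date in (b) for deceased subjects as well, from direct evidence only: a non-zero dose given, a scan, a laboratory, vital-sign, ECG or PK measurement, or a survival contact that reports the subject alive. SAP Table 2-1 should not be used unchanged. It admits the end-of-treatment page date without condition, zero-dose records, adverse event end dates and survival entries with unknown status. For a subject who has died, none of these proves life on that date.

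The cost is one short paragraph in the SAP, a restricted version of an existing derivation, and one maximum in the program. No new data are needed.
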